7.6.2.2 Change from Baseline for Selected Laboratory Parameters Over Time

Scheduled laboratory measurements and corresponding change from baseline values will be summarized by treatment and nominal visit for each laboratory test for the As Treated analysis population using descriptive statistics (see [section 7.1.3](#)). Visit windows are provided in [Section 8.1](#) in order to link each laboratory test to a scheduled visit. The following laboratory parameters will be analyzed:

- Hemoglobin
- Hematocrit
- Total leukocyte count
- Basophils Count
- Eosinophils Count
- Lymphocytes Count
- Monocytes Count
- Neutrophils Count
- Platelet count
- Aspartate aminotransferase (AST)
- Alanine aminotransferase (ALT)
- Total bilirubin
- Direct bilirubin
- Alkaline phosphatase
- Lactate dehydrogenase (LDH)

- Creatinine
- Blood Urea Nitrogen (BUN)
- Uric acid
- glucose at fasting state
- Total Protein
- Albumin
- Sodium
- Potassium
- Chloride
- Calcium
- Phosphorus
- Magnesium
- Creatine kinase
- Total cholesterol at fasting state
- HDL-cholesterol at fasting state
- LDL-cholesterol at fasting state
- Triglycerides at fasting state
- ESR (local test)
- hsCRP
- Urine Protein
- Urine Glucose
- Urine Blood
- Urine Specific gravity
- Urine pH

As per protocol all laboratory parameter mentioned above are part of the safety laboratory test panel and are supposed to be assessed with the subject at fasting state. However for analysis purposes all data will be considered for analysis, even if the subject was not in a fasting state, unless if it is mentioned otherwise above. In these cases, only those measurement where the subject was on fasting state will be considered for analysis.

7.6.2.3 Pregnancy Test Results

A by-subject listing of positive pregnancy test results will be provided using the As-treated analysis population.

7.6.3 Electrocardiogram

Summary statistics (n, mean, standard deviation, median, minimum, and maximum) will be presented for each ECG parameters and the corresponding changes from baseline by treatment

and visit. ECG readings will be evaluated by the Investigator and abnormalities, if present, will be listed.

The frequency distribution of subjects' maximum recorded post-dose QTcF, PR, QRS and ΔQTcF (see section 8.19) will be tabulated by treatment and summarized within the CSR text for the ranges in Table 7.6.3-2. Individual QTcF, PR, QRS or ΔQTcF values meeting these criteria will be flagged in the data listing.

Table 7.6.3-2: Electrocardiogram Parameter Categorization

Parameter	Categorization
QTcF (msec)	≤ 450
	450 < to ≤ 480
	480 < to ≤ 500
PR (msec)	> 500
	≤ 200
QRS (msec)	> 200
	≤ 120
Change from baseline in QTcF (msec)	> 120
	≤ 30
	30 < TO ≤ 60
	> 60

7.6.4 Vital Sign

Vital signs parameters (systolic blood pressure, diastolic blood pressure, heart rate, respiratory rate and body temperature) will be listed. Summaries of vital sign parameters will be provided for each vital sign parameter at corresponding visits by treatment and respective changes from baseline. Subjects with vital signs outside of a pre-specified range will also be listed.

The following criteria will be used to determine vital sign results that are outside of a pre-specified range, where changes from baseline are based on matched postural positions and are calculated as parameter value - baseline parameter value:

Table 7.6.4-2: Vital signs criteria

Vital sign	Criteria
Heart Rate(bpm)	Value > 100 and change from baseline > 30, or Value < 55 and change from baseline < -15
Systolic BP(mmHg)	Value > 140 and change from baseline > 20, or Value < 90 and change from baseline < -20
Diastolic BP(mmHg)	Value > 90 and change from baseline > 10, or Value < 55 and change from baseline < -10

Table 7.6.4-2: Vital signs criteria

Vital sign	Criteria
Respiration(breaths/min)	Value > 16 or change from baseline > 10
Temperature (°C)	Value > 38.3°C or change from baseline > 1.6°C

7.6.5 Physical Examination Findings

All physical examination abnormal findings will be listed per subject by visit.

[REDACTED]

7.8 Outcomes Research Analyses

The outcome research analysis endpoints described in this section are considered as secondary endpoints. For their analysis, no multiplicity adjustment will be applied and no p-values will be provided.

Descriptive summary statistics (see section 7.1.3) will be provided for absolute value and change (or percent change) from baseline to all assessments as described in the protocol for primary measures the following outcome research assessments:

- Numeric Rating Scale (NRS) scores for mouth, eye and vaginal dryness (see [section 8.12](#)). Each of these scores will be analyzed separately.
- Subject global assessment of disease activity (SubGDA) and physician global assessment of disease activity (phyGDA) will be analyzed separately (see [section 8.13](#))

- Short Form - 36 acute (SF-36 acute) (see [section 8.14](#)). Both the physical and mental scales as well as the individual sub-scales will be analyzed.
- Female Sexual Function Index (FSFI) (see [section 8.15](#)). Both the full scale score and the individual domain scores will be analyzed.
- Work participation and activity impairment questionnaire (WPAI) (see [section 8.16](#)). Percent work time missed due to health, percent impairment while working due to health, percent overall work impairment due to health and percent activity impairment due to health will be analyzed.
- PROMIS Fatigue Short Form 8a (see [section 8.17](#)).

If deemed necessary after observing results from the analyses described above, the MMRM method or other modelling methods may be applied to changes from baseline in primary measures (e.g., total scores) of the above outcome research measures.

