8.4.6 Outcomes Research Analyses

Descriptive summary statistics will be provided for absolute value and change (or percent change) from baseline in primary measures as well as eligible sub-domain scores for all the following outcome research assessments:

- Numeric Rating Scale (NRS) scores for mouth, eye and vaginal dryness
- Subject global assessment of disease activity (SubGDA) and physician global assessment of disease activity (phyGDA)
- Short Form - 36 acute (SF-36 acute)
- Female Sexual Function Index (FSFI)
- Work participation and activity impairment questionnaire (WPAI)
- PROMIS Fatigue Short Form

In addition, the MMRM method or other modelling methods may be applied to changes from baseline in primary measures (eg, total scores) of the above outcome research measures whenever appropriate. Details for those analyses will be provided in the statistical analysis plan.

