APPENDIX 4	DOCUMENT HISTORY	67
10	REFERENCES.....	68

LIST OF TABLES

Table 7.1.2-1:	Formulae Used to Transform Back onto the Original Scale the Estimates of Percent Change from Baseline Analyzed as Geometric Mean.....	21
Table 7.1.5.2-2:	Contrast Coefficients for the treatment-by-baseline interaction for visit 85 estimates	24
Table 7.3.2-2:	Demographic and Baseline Characteristics	28
Table 7.6.3-2:	Electrocardiogram Parameter Categorization	39
Table 7.6.4-2:	Vital signs criteria	39
Table 7.9.1-2:	Categorical classifications for ANA.....	42
Table 8.2.2-1:	Visit Windows for Double-Blind Treatment Period	45
Table 8.2.2-2:	Visit Windows for the Follow-Up Period.....	46
Table 8.6-2:	The EULAR Sjögren's Syndrome Disease Activity Index (ESSDAI) scoring algorithm.....	50
Table 8.15-2:	Scoring algorithm for Female Sexual Function Index (FSFI)	53
Table 8.17-2:	PROMIS Fatigue 8a Short Form Conversion Table	54

LIST OF FIGURES

Figure 1-1:	Pathogenic Mechanisms in Sjögren's Syndrome.....	9
Figure 2.1-1:	Study Design Schematic	14
Figure 8.3-1:	The EULAR Sjögren's Syndrome Patient Reported Index (ESSPRI).....	51

Schedule of Analyses:

The following analyses will be performed:

- One interim analysis will be conducted when at least 30 subjects reach Week 12 (complete 12 weeks of treatment) and complete the specified assessments for the Week 12 ESSDAI score. The interim analysis will be conducted in a fully blinded manner such that treatment group assignments of study subjects are not known and are not used in any manner in the analysis. Specifically, a blinded examination of the variance of the primary endpoint will be performed and compared to the assumption used in planning the study. If this comparison suggests the initial assumption is substantially too low, the total study sample size may be increased by up to 45 additional subjects (i.e., to a maximum of 120 subjects in total) to maintain adequate study power.^{24,25,26} Regardless of the outcome from the blinded examination of variability, the study sample size will not be decreased. Details on the blinded sample size re-estimation will be given in the statistical analysis plan.
- A final analysis will be performed after the last treated subject in the study reaches the end of the study.

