4.2 Secondary Endpoint(s)

- Change from baseline in ESSPRI score at Week 12
- Proportions of subjects with ≥ 3 points of improvement from baseline in ESSDAI at Week 12
- Proportions of subjects with ≥ 1 point of improvement from baseline in ESSPRI at Week 12
- Proportion of subjects with both ≥ 3 points improvement in ESSDAI and ≥ 1 point improvement in ESSPRI from baseline at Week 12
- Change from baseline in:
 - ESSDAI scores at Week 4 and Week 8
 - ESSPRI scores at Week 4 and Week 8
 - ESSPRI individual component (Dryness, Fatigue, and Pain) scores at Weeks 4, 8, and 12
 - Unstimulated and stimulated salivary flow rate at Weeks 4, 8, and 12
 - Ocular surface staining, Schirmer’s test, and the tear break-up time test at Weeks 4, 8, and 12
- Safety and tolerability of lulizumab or BMS-986142 in subjects with moderate to severe pSS, as measured by AEs, laboratory parameters, vital signs, physical exams, and ECGs
- Subject and physician assessments of disease activity:
 - Numeric rating scale (NRS) for mouth, eye and vaginal dryness
 - Subject global assessment of disease activity (SubGDA) and physician global assessment of disease activity (phyGDA),
 - Short Form-36 (SF-36)
 - Female Sexual Function Index (FSFI)
 - Work participation and activity impairment questionnaire (WPAI)
 - PROMIS Fatigue Short Form
- Trough concentrations of BMS-931699 and BMS-986142 at time points specified in protocol Section 5.5

[REDACTED]

- **Double-blind treatment and follow-up periods:** It starts at the time of the first dose of blinded treatment and continues up to 42 days post last dose.

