7.1.3 Descriptive Summaries of Continuous Variables

Descriptive summaries of continuous variables in terms of baseline values, change or percent change from baseline values will be provided by treatment group and overall, as applicable. These summaries may include the estimations of means, medians, standard deviations and ranges, as applicable.

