7.5.2.2 Continuous Endpoints

The change from baseline in the following continuous endpoints will be analyzed with mixed effects model with repeated measures (MMRM) as described in [section 7.1.5.1](#). The model will

include all assessments for each parameters as defined in the protocol. Nominal p-values will be provided for those endpoints that are defined as secondary endpoints in the protocol.

- Change from baseline in ESSDAI scores at each time point of assessment. The change from baseline at Week 4, 8, are defined as secondary endpoints as per protocol. The change from baseline at Week 12 is the primary efficacy endpoint (see [section 7.5.1](#)). See [Section 8.6](#) for calculation of ESSDAI.
- Change from baseline in ESSDAI domain scores at each time point of assessment. This is considered as an exploratory efficacy endpoint. The scores for the ESSDAI domains Glandular, Articular, Hematological, Biological, Lymphadenopathy, Pulmonary and Constitutional will be analyzed with mixed effect models. The scores for the ESSDAI domains Central Nervous System (CNS), Cutaneous, Muscular, Peripheral Nervous System (PNS) and Renal will be analyzed with summary statistics. See [Section 8.6](#) for calculation of ESSDAI domain scores.
- Change from baseline in ESSPRI scores at each time point of assessment. The change from baseline at Week 4, 8, and, 12 are defined as secondary endpoints as per protocol. See [Section 0](#) for calculation of ESSPRI.
- Change from baseline in score of each individual ESSPRI components (Dryness, Fatigue, and Pain) at each time point of assessment. The change from baseline at Weeks 4, 8, and 12 are defined as secondary endpoints as per protocol. See [Section 0](#) for calculation of individual ESSPRI components.
- Change from baseline in mouth dryness as measured by unstimulated and stimulated salivary flow rate at Weeks 4, 8, and 12. See [Section 8.8](#) for calculation of salivary flow rate.
Change from baseline in eye dryness as measured by ocular surface staining (see [section 8.11](#)), Schirmer's test (see [section 8.9](#)), and tear break-up (see [section 8.10](#)) time test at Weeks 4, 8, and 12. These analysis will be repeated for each eye separately and combining information for the two eyes taking the average of test values on the same visit.

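### SAP 7.8 lets the choice and method of modelling for the outcomes research secondary endpoints be made after by-arm results are seen, so modelled between-arm estimates may exist only for a selected subset

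*SAP*

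**What the plan says.** SAP 4.2 lists these measures as secondary endpoints under "Subject and physician assessments of disease activity": NRS scores for mouth, eye and vaginal dryness, SubGDA, phyGDA, SF-36, FSFI, WPAI and PROMIS Fatigue. SAP 7.8 repeats that they are secondary and states that "no multiplicity adjustment will be applied and no p-values will be provided".

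The only firm commitment in SAP 7.8 is to descriptive statistics. SAP 7.1.3 defines these as means, medians, standard deviations and ranges, where "change or percent change from baseline values will be provided by treatment group and overall". No between-arm difference or interval is part of that output. Modelling comes next, and only conditionally: "If deemed necessary after observing results from the analyses described above, the MMRM method or other modelling methods may be applied".

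Protocol 8.4.6 also makes modelling optional. It may be applied to the primary measures "of the above outcome research measures whenever appropriate", and the protocol adds: "Details for those analyses will be provided in the statistical analysis plan".

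On timing, the one interim analysis is blinded and confined to the variance of ESSDAI. By-arm results for these endpoints therefore first appear at the end: "A final analysis will be performed after the last treated subject in the study reaches the end of the study".

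**The concern.** The decision to model, the choice of measure and the choice of method all fall after the by-arm summaries have been read. The protocol's condition was appropriateness, which can be judged blind. The SAP replaces it with a condition on results and does not supply the promised detail.

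The model is the only planned route to a treatment difference adjusted for baseline and stratification factors. If it is run for the measures whose summaries favour a drug, the reported differences are the upper tail of a set. Their intervals then no longer have 95% coverage. Measures passed over would have no adjusted estimate, although Protocol 5.7 schedules the NRS scores, SubGDA and phyGDA at six on-treatment visits (Days 15, 29, 43, 57, 71, 85) and the other instruments at three (Days 29, 57, 85).

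The SAP is also uneven. SAP 7.5.2.2 commits MMRM unconditionally to seven ESSDAI domain scores that it calls exploratory, while these named secondary endpoints have no fixed model.

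**Working it through.** **The plan's own figures.** The documents give no operating characteristic for the SAP 7.8 endpoints. The sample size per arm comes from the primary endpoint: 25 per arm, difference 3, SD 3.2, two-sided 0.05. The noncentral-t power is 90.1%, against about 90% stated. With 40 per arm and SD 4.8 it is 78.8%, against 79% stated. Both reproduce.

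**Inputs for the illustration.**
- Candidate headline scores, counted from the SAP 7.8 list: 3 NRS + SubGDA + phyGDA + 2 SF-36 summaries + FSFI total + 4 WPAI percentages + PROMIS Fatigue = 13.
- Two active arms against one shared placebo arm: 13 × 2 = 26 Week 12 contrasts.
- 25 per arm (40 at the maximum sample size), with SD known and set to 1.
- No true effect of either drug.
- Correlation between measures: not in the documents; assumed, and varied from 0 to 0.7.

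**Formula.** The standard error of one contrast is √(2/25) = 0.283 SD, so the 95% half-width is 1.96 × 0.283 = 0.554 SD. If only the most favourable contrast is modelled, its interval misses the true value of zero when the largest standardised difference exceeds 1.96.

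**Closed-form benchmark.** If all 26 contrasts were independent, coverage would be 0.975^26 = 51.8%. The shared placebo arm rules out independence, so the contrasts were simulated (200,000 runs per row).

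| Assumed correlation | Expected difference, 25 per arm (SD) | Coverage, 25 per arm | Expected difference, 40 per arm (SD) | Coverage, 40 per arm |
|---|---|---|---|---|
| 0 | 0.55 | 55% | 0.43 | 55% |
| 0.3 | 0.48 | 66% | 0.38 | 66% |
| 0.5 | 0.43 | 73% | 0.34 | 73% |
| 0.7 | 0.36 | 80% | 0.29 | 80% |

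The true difference is zero in every row, so the expected difference is all bias. A larger sample shrinks the bias in SD units but does not restore coverage.

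**With a fixed rule.** An estimate reported whatever its result has zero bias in this setting and an interval with nominal 95% coverage. The change affects no sample size or power figure.

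**The case against.** The case on the other side is substantial, and most of it limits the point.

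- **Scope.** A reader might infer that every patient-reported secondary endpoint is affected. That is not so. SAP 7.5.2.2 fixes MMRM with nominal p-values for ESSPRI and its components ("Change from baseline in ESSPRI scores at each time point of assessment").
- **Certainty and motive.** A reader might infer that measures will be picked because they look promising. The clause is permissive: it allows modelling all of them or none, and in either case no selection among measures arises. It states no motive.
- **Suppression.** No measure is hidden. Every one gets by-arm summaries, from which a crude difference can be derived.
- **Departure from the protocol.** No promised model was withdrawn, since Protocol 8.4.6 was already optional. The MMRM itself is fully specified in SAP 7.1.5.1. What is missing is a trigger free of results, a list of eligible measures and a meaning for other methods.
- **Size.** It is tempting to cite 1 − 0.95^26 = 74% as the harm. That is the chance that at least one of 26 independent null intervals excludes zero when all are reported, so it measures multiplicity, not selection. Reporting ten scores for two drugs would still give 1 − 0.95^20 = 64% on the same assumption.
- **No p-values.** This limits over-claiming but does not cure the problem, because a selected estimate and its interval are distorted without one.

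The SAP's per-instrument convention sections (8.12 to 8.17) cannot be read in the public copy. Their titles in the contents list make a modelling rule there unlikely. All these limits stand; the result-dependent sentence in SAP 7.8 remains.

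**Conclusion.** The concern holds for the SAP 7.8 measures only. The SAP states a results-driven rule for modelling named secondary endpoints, where the protocol had left modelling optional but not tied to results. Modelled between-arm estimates may therefore be a selected subset. If selection follows apparent benefit, they are biased away from zero and their intervals under-cover.

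The figures of 0.55 to 0.36 SD and 55% to 80% coverage are a worst case and not a forecast. They rest on the count of 13 scores, the assumed correlations, no true effect, modelling of only the single best contrast, and 25 subjects on every measure. The vaginal dryness scale is for females only (Protocol 5.7), so its numbers would be smaller and its estimates noisier. Freedom over visit or method could add to the selection and is not counted.

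A reader might infer that the trial's main conclusion is at risk. The documents do not support that: the Week 12 ESSDAI model and its Hochberg adjustment are fixed in SAP 7.5.1 and do not depend on this clause. The consequence is modest, but the plan should be corrected.

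**What to change.** Before unblinding, delete the condition in SAP 7.8. State that the SAP 7.1.5.1 MMRM, with each score's own baseline as covariate, will be run whatever the descriptive results for ten scores: the three NRS scores, SubGDA, phyGDA, the SF-36 physical and mental summaries, FSFI total, PROMIS Fatigue and WPAI activity impairment. Report every difference from placebo with its 95% interval and no p-value. Keep the WPAI work items and all sub-domain scores descriptive, and say so in advance. Label any other model post hoc.

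At minimum, if the sponsor prefers to keep these endpoints descriptive only, the SAP should say that and label any later model post hoc. This also removes the defect and stays within Protocol 8.4.6.

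The cost is SAP wording and about ten runs of an existing model. Sample size, visits and data collection do not change.

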7.9 Biomarker Analyses

The table is mostly obscured by black redaction boxes. Visible elements include a header row with two columns, and several rows of data with varying lengths of redaction. The table is bounded by double horizontal lines at the top and bottom.

7.9.2 Biopsies

The focus scores of lip or parotid gland biopsies and the corresponding changes from baseline will be summarized by treatment and visit using descriptive statistics (see [section 7.1.3](#)). Visit windows are provided in [Section 8.1](#) in order to link each score test to a scheduled visit.

A subject listing of all lip or parotid gland biopsy findings will be provided.

The table is mostly obscured by black redaction boxes. Visible elements include a header row with two columns, and several rows of data with varying lengths of redaction. The table is bounded by double horizontal lines at the top and bottom.

[REDACTED]

7.11 Interim Analyses

One interim analysis will be conducted when at least 30 subjects reach Week 12 (complete 12 weeks of treatment) and complete the specified assessments for the Week 12 ESSDAI score. The interim analysis will be conducted in a fully blinded manner such that treatment group assignments of study subjects are not known and are not used in any manner in the analysis. Specifically, a blinded examination of the variance of the primary endpoint will be performed and compared to the assumption used in planning the study. If this comparison suggests the initial assumption is substantially too low, the total study sample size may be increased by up to 45 additional subjects (i.e., to a maximum of 120 subjects in total) to maintain adequate study power.^{28 29 30} Regardless of the outcome from the blinded examination of variability, the study sample size will not be decreased.

The blinded examination of the variance will be based on the following assumptions:

- the placebo adjusted change from baseline at Week 12 for both active treatment arms (lulizumab or BMS-986142) will be 3 ESSDAI points
- the change from baseline at Week 12 will be the same for both active treatment arms.

The calculation of the blinded examination of the variance will include randomized subjects who received at least one dose of study drug with non missing ESSDAI assessment both for baseline and Week 12. Subjects will be considered for analysis if their Week 12 assessment occur while on double-blind study medication.

The estimate of the blinded examination of the variance $S_{blinded}^2$ will be computed using the formula mentioned by Kieser and Friede (2000)³⁶:

$$S_{blinded}^2 = S_{pooled}^2 - \frac{n}{n-1} \cdot \sum_{i=1}^3 (\mu_i - \bar{\mu})^2$$

where:

- S_{pooled}^2 is the variance of change from baseline at Week 12 in ESSDAI as calculated based on all subjects included in the interim analysis
- n is the number of subjects included in the interim analysis (across all treatment groups)
- μ_i is the assumed change from baseline at Week 12 for each of the 3 arms
- $\bar{\mu}$ is the assumed overall mean. For this calculation it is assumed to be average of μ_i across all treatment groups

Since μ_i and $\bar{\mu}$, the $\sum_{i=1}^3 (\mu_i - \bar{\mu})^2$ will be approximated by the term below:

$$\begin{aligned} & \left(\xi_{Lulizumab} - \frac{\xi_{Lulizumab} + \xi_{BMS-986142} + \xi_{Placebo}}{3} \right)^2 + \\ & + \left(\xi_{BMS-986142} - \frac{\xi_{Lulizumab} + \xi_{BMS-986142} + \xi_{Placebo}}{3} \right)^2 + \\ & + \left(\xi_{Placebo} - \frac{\xi_{Lulizumab} + \xi_{BMS-986142} + \xi_{Placebo}}{3} \right)^2 \end{aligned}$$

where

$$\xi_{Lulizumab} = \xi_{BMS-986142} = 3 \text{ ESSDAI points and } \xi_{Placebo} = 0.$$

The common standard deviation will be estimated based on the estimate of the blinded examination of the variance.

The common standard deviation will be compared against the initial study assumptions for sample size estimation (see [section 5](#)). Would it be substantially larger than the initially planned, the sample size for the study will be re-estimated taking into consideration the maintenance of adequate power for the study (see [section 5](#)).

The final decision on sample size and power for this study will be made by BMS senior management.

